8. EFFICACY ANALYSIS

8.1 Primary Efficacy Analysis (3M Oral Rinse vs. Vehicle Control)

Performance of the 3M Oral Rinse will be assessed based on two primary endpoints. Statistical analysis will be performed on the PI and GI scores at 6-months using an ANCOVA with treatment as the factor and baseline score as a covariate. The success criterion for the study will be based on the single comparison between the 3M Oral Rinse group and the vehicle control group. The primary efficacy analysis will exclude data from the other two treatment groups, namely, the PerioShield (predicate) and the water control groups.

Significance of the overall treatment effect will be assessed by the p-value associated with the F-test statistic for the treatment group. The level of significance will be two-sided alpha of 0.05. The main null hypothesis of interest to support that 3M Oral Rinse reduces plaque and gingivitis is as follows:

$$H_0: \mu_{3M \text{ Oral Rinse}} \geq \mu_{\text{Vehicle}} \text{ versus } H_A: \mu_{3M \text{ Oral Rinse}} < \mu_{\text{Vehicle}}$$

Both primary endpoint comparisons will be based on the intent-to-treat (ITT) data set. The study will be considered successful if both primary endpoints are met.

In the event of a significant demographic or baseline variable, the primary efficacy ANCOVA model will be expanded to include this significant variable as a covariate or factor in the model. Statistical models with interaction terms or subgroup analyses will be explored if appropriate to help further understand the treatment effect.

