3.3 Blinding and Blinding Assessment

Before data lock and final study data analysis, the biostatistician will remain blinded to treatment assignment. The final data review and data classification meeting will be conducted before data lock and statistical programming will occur using dummy treatment assignments.

The Principal Investigator and clinical examiners will be blinded to the treatment products. No clinical examiners will see the allocated rinse assigned per the randomization schedule. Due to the rinse packaging differences and to maintain the blind, all study products will be placed in a non-transparent container. Subjects will be told not to open the container until they return to their home and to bring study supplies back to their next scheduled appointment in the same container. Only the study coordinator at the site will know the randomization assignment.

Each subject will be asked to indicate to what treatment he or she thinks they have been assigned. This assessment will be done immediately after the first dose and at the end-of-study visit. The subject will indicate if he or she thinks the treatment assigned is (a) the new 3M Oral Rinse, (b) one of the control rinses, or (c) does not know or cannot make an educated guess. The responses to the blinding assessment questionnaire at both time points will be summarized by the randomized treatment group.

4. Efficacy Endpoints

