7.3 Baseline and Demographic Characteristics

Demographic variables will be examined to assess comparability of the treatment groups prior to the initiation of treatment. Characteristics evaluated include age, sex, race, ethnicity and tobacco use status. An overall Fisher's Exact test (discrete variables) or ANOVA model (continuous variables) will be used to compare each demographic or baseline variable among all four treatment groups.

Descriptive summary statistics will be provided for demographic characteristics for each treatment group and overall. For age, the number of subjects, mean, standard deviation, median, minimum and maximum will be provided. For sex, race, ethnicity and tobacco use status, the number and percentage of subjects in each demographic category will be summarized.

In addition, screened subjects participating in the wash-out period before randomization will be summarized by demographic variables.

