9.1 Adverse Events

All adverse events (AEs) occurring after initiation of study treatment (treatment emergent AEs) will be summarized by severity, relatedness, overall and treatment group. AEs occurring during the screening period will be summarized separately. All AEs will be classified using the MedDRA dictionary.

All verbatim descriptions will be listed for all AEs, along with information regarding onset, duration, severity, relationship to treatment, and action taken.

Serious adverse events will be summarized and presented according to nature, time to onset, duration, relationship to treatment and outcome.

First, an overall Fisher's Exact test will be carried out to compare each safety parameter among all four treatment groups. If this overall test is significant ($p\text{-value} \leq 0.05$), pairwise comparisons will be carried out to compare the 3M Oral Rinse and the vehicle control. Each active vs vehicle comparison will be carried out at an alpha level of 0.05.

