11.3 Primary Efficacy Analyses with 3M Oral Rinse and Vehicle Control

Performance of the 3M Oral Rinse (3M OR) will be assessed based on two primary endpoints. Statistical analysis will be performed on the PI and GI scores at 6-months using an ANCOVA with treatment as the factor and baseline score as a covariate.

The success criterion for the study will be based on the single comparison between the 3M Oral Rinse group and the vehicle control group. The primary efficacy dataset will exclude data from the other two treatment groups, namely, the PerioShield (predicate) and the water control groups.

Significance of the overall treatment effect will be assessed by the p-value associated with the F-test statistic for the treatment group. The level of significance will be two-sided alpha of 0.05.

The main null hypothesis of interest to support that 3M Oral Rinse reduces plaque and gingivitis is as follows:

$$H_0: \mu_{3M \text{ Oral Rinse}} \geq \mu_{\text{Vehicle}} \text{ versus } H_A: \mu_{3M \text{ Oral Rinse}} < \mu_{\text{Vehicle}}$$

Both primary endpoint comparisons will be based on the intent-to-treat (ITT) data set. The study will be considered successful if both primary endpoints are met.

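### The ANCOVA that decides success gains covariates by an undefined significance trigger; its natural source, SAP 7.3, tests all four arms although only two are analysed

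*SAP*

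**What the plan says.** Protocol 11.3 defines the primary analysis of PI and GI at 6 months "using an ANCOVA with treatment as the factor and baseline score as a covariate" and stops there. SAP 8.1 repeats that model and restricts it to two arms: "The primary efficacy analysis will exclude data from the other two treatment groups". It then adds a rule that the protocol does not contain: "In the event of a significant demographic or baseline variable, the primary efficacy ANCOVA model will be expanded to include this significant variable". The only level in SAP 8.1, "The level of significance will be two-sided alpha of 0.05", belongs to the F-test for treatment.

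SAP 7.3 is the one place where baseline variables are tested. An overall Fisher's exact test or ANOVA "will be used to compare each demographic or baseline variable among all four treatment groups". It gives no level, no consequence and no pointer to 8.1. Its list is open-ended: "Characteristics evaluated include age, sex, race, ethnicity and tobacco use status".

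By contrast, SAP 9.1 does state a threshold where it wants a screen: "an overall Fisher's Exact test will be carried out to compare each safety parameter among all four treatment groups", with p ≤ 0.05 opening the next step.

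On blinding, SAP 3.3 says that "statistical programming will occur using dummy treatment assignments" and keeps the biostatistician blinded until data lock.

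**The concern.** Success depends on this one model, run once for PI and once for GI. A mandatory expansion with no stated test or level leaves the model open.

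If SAP 7.3 is the trigger, two further problems follow. First, in a properly randomized trial its tests detect only chance imbalance, so chance picks the covariates. That imbalance may lie wholly in the PerioShield or water arm, which contribute nothing to the comparison. Second, the tests need the real allocation. With programming done on dummy assignments, the final form of the deciding model is known only after unblinding. At stake is whether a reader can tell from the SAP, before unblinding, which model will decide the trial.

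**Working it through.** **Inputs from the documents.** 34 per group for 90% power, difference 0.40, SD 0.5, one-sided 0.025, 50 per group recruited (SAP 6.1); five named characteristics (SAP 7.3); two arms in the deciding model (SAP 8.1).

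**Assumptions.** Trigger level 0.05; independent variables; each explaining 2% of outcome variance, or 9.5% as a high case. The high value is 0.308² = 0.095, from the age-GI correlation in Protocol 4.1, applied to all five variables.

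**1. The plan's own figure.** By normal approximation n = 2 × (1.960 + 1.282)² × (0.5/0.4)² = 2 × 10.51 × 1.5625 = 32.8, so 33. By the noncentral t, power is 89.3% at 33 and 90.2% at 34, so the stated 34 is right. At 50 per arm, power is 97.7% per endpoint.

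**2. How often chance fires the rule.** 1 − 0.95⁵ = 22.6%. The range over what the SAP leaves open: 41.0% for five variables at 0.10, and 33.7% for eight variables at 0.05.

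**3. Does the four-arm screen see the relevant imbalance?** In 400,000 simulated four-arm trials with no true imbalance (one continuous variable, 50 per arm), the 3M-vehicle difference had p<0.05 in 36.6% of trials with a significant four-arm test. Each event alone has probability 0.05, so both occur together in 0.366 × 0.05 = 1.8% of trials, and the same 36.6% holds in the other direction. Hence 1 − 0.366 = 63.4% of 3M-vehicle differences at p<0.05 do not trigger the rule. For differences at p<0.01, about 16% are missed.

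**4. Effect on the decision.** The rule, read as the 7.3 tests at 0.05, was compared with the unexpanded model by simulation: 30,000 trials per setting at effect 0 and 10,000 at each other effect. Age was continuous; prevalences were assumed as sex 50%, ethnicity 30%, tobacco use 15%, race 50/20/20/10%; chi-square stood in for Fisher's exact test. Results are per endpoint.

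| | 2% each | 9.5% each |
|---|---|---|
| One-sided error, unexpanded model | 2.52% | 2.53% |
| One-sided error, four-arm rule | 2.50% | 2.29% |
| Verdict changed, effect 0.40 | 0.35% | 0.74% |
| Verdict changed, effect 0.20 | 2.09% | 4.18% |

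The Monte Carlo standard error of the error rates is about 0.09 percentage points. The effect of 0.20 is not a planning value; it is half the planned effect.

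**5. Four-arm against two-arm imbalance.** Had the sponsor meant imbalance between 3M and vehicle only, the selected covariates would differ from the four-arm choice in about 28% of trials. Even taking the more favourable of these two after seeing results gives a one-sided error of about 2.3% to 2.6%, so no inflation is detectable.

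**The case against.** The best defence is that the two sections belong together. SAP 8.1 reuses the wording of 7.3 for the variables concerned, 7.3 is the only place that tests them, and its purpose is comparability of the groups. A level of 0.05 is the obvious inference, given the treatment test in 8.1 and the screens in SAP 9.1 and 9.2. This stands as the natural reading. It still leaves the level unstated and a four-arm test choosing covariates for a two-arm model.

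It is also fair to say that under this reading selection uses baseline data and allocation only. Outcomes play no part, so the choice cannot be tuned to the result. The SAP was approved before enrolment, is open to amendment only before unblinding (Introduction), and requires changes of method to be reported (section 6). These points stand and explain why error is not inflated.

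A reader might go further and count association with outcome as a third meaning of *significant*. The three meanings would then rarely agree (different covariates in 86% to 100% of trials), and picking the best after the fact would give 3.4% to 4.2% one-sided error, or 3.7% to 4.5% if a 0.10 level were also allowed. The documents do not support this. No section describes screening covariates against the outcome or a 0.10 level, and those figures depend on them.

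Finally, Protocol 4.1 reports that age, sex and race are related to GI, so wanting to adjust is reasonable. That argues for naming the covariates in advance, not for letting a significance test choose them.

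**Conclusion.** The concern holds at low severity. The success model can change according to a test whose level is unstated and which is partly driven by arms outside the analysis. Its final form is known only once allocation is known, and Protocol 11.3 has no such step. A reader might infer that the trial's false-positive rate is therefore compromised; the calculations do not show that. Under the 7.3 reading, one-sided error is at or slightly below 0.025, and an endpoint's verdict changes in about 0.35% to 0.74% of trials at the planned effect. Because both endpoints must succeed, study-level error is lower still unless the other endpoint truly works.

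The sizes rest on the assumed 0.05 level, independence, the prevalences and the prognostic strengths. The 9.5% case is generous: five such variables would explain 47.5% of outcome variance, and the baseline score already in the model should absorb part of that. Fisher's exact test is conservative, so the true firing rate may be somewhat below 23%. The textual gap depends on none of these assumptions.

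**What to change.** In SAP 8.1, remove the significance-triggered expansion. State that treatment plus the endpoint's own baseline score is the sole deciding model for both PI and GI, as in Protocol 11.3. If the sponsor wants further adjustment, name a fixed list of covariates before unblinding, to be used whatever the baseline tests show. Report the SAP 7.3 comparisons descriptively. Label any other adjusted model as supportive and unable to alter the success decision.

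The cost is a wording change in the SAP. No new data are needed, and 34 and 50 per group stay as they are. The downside is that chance imbalance is then addressed only in supportive analyses, and some precision may be forgone if no covariates are named. With 97.7% power per endpoint at 50 per arm under the planning assumptions, that loss is easily borne.

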8.2 Secondary Efficacy Analysis (3M Oral Rinse vs. Vehicle Control)

Secondary efficacy hypotheses will be tested in a fixed sequential order, conditional on the expected significance of the primary analyses. The fixed-sequence testing of a subsequent hypothesis will be conditional on the significant testing of the previous hypotheses. The sequential order of testing will preserve the one-sided alpha of 0.025 and is outlined as follows:

1. Modified Quigley-Hein Plaque Index (PI) at 3 months between the 3M Oral Rinse and the Placebo Vehicle Control
2. Löe-Silness Gingivitis Index (GI) at 3 months between the 3M Oral Rinse and the Placebo Vehicle Control
3. Eastman Interdental Bleeding Index at 6 months between the 3M Oral Rinse and the Placebo Vehicle Control
4. Eastman Interdental Bleeding Index at 3 months between the 3M Oral Rinse and the Placebo Vehicle Control.

8.3 Secondary Efficacy Analysis with all Four Treatment Groups

All pairwise comparisons involving the four treatment groups, namely the 3M Oral Rinse, vehicle control, PerioShield predicate and water control groups, will be carried out with the PI and GI endpoints at 6 months. Analyses will be performed using the ANCOVA model and the p-values will be adjusted using the Tukey method.

9. SAFETY ANALYSIS

Safety variables will include adverse events, abnormal soft and hard oral tissue, and reported side effects.

9.1 Adverse Events

All adverse events (AEs) occurring after initiation of study treatment (treatment emergent AEs) will be summarized by severity, relatedness, overall and treatment group. AEs occurring during the screening period will be summarized separately. All AEs will be classified using the MedDRA dictionary.

All verbatim descriptions will be listed for all AEs, along with information regarding onset, duration, severity, relationship to treatment, and action taken.

Serious adverse events will be summarized and presented according to nature, time to onset, duration, relationship to treatment and outcome.

First, an overall Fisher's Exact test will be carried out to compare each safety parameter among all four treatment groups. If this overall test is significant ($p\text{-value} \leq 0.05$), pairwise comparisons will be carried out to compare the 3M Oral Rinse and the vehicle control. Each active vs vehicle comparison will be carried out at an alpha level of 0.05.

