3.2 Randomization

The treatment groups consisting of four different oral rinses will be assigned to the letter labels A, B, C, D.

The randomization was created by a biostatistician who will not be involved in the analysis of the study data, keeping the study biostatistician blinded to the randomization schedule. The randomization schedule created treatment assignments for 216 subjects, 16 extra over the protocol specified sample size to account for contingencies. The randomization ratio was 1:1:1:1 among the four treatment groups.

Details of the randomization scheme followed, and the protocol deviations related to randomization errors will be documented in the final study report.

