6.1 Determination of Sample Size

The sample size was estimated based on GI and PI scores from preliminary clinical study data and the literature. It is estimated that 34 subjects per group will provide 90% power to detect a difference of 0.40 (standard deviation of 0.5) in the GI and PI scores using a 1-sided 0.025 alpha level. To account for possible dropouts, a sample size of 50 subjects per group will be recruited.

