11.6 Safety Analysis

Safety variables will include adverse events, abnormal soft and hard oral tissue, and reported side effects. First, an overall test will be carried out to compare each safety parameter among all four treatment groups. If this overall test is significant ($p\text{-value} \leq 0.05$), pairwise comparisons will be carried out to compare the 3M Oral Rinse and the vehicle control. Each active vs vehicle comparison will be carried out at an alpha level of 0.05.

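### The only safety comparison the plan names, 3M rinse versus vehicle, is made only after a significant four-arm test, so a nominally significant difference can go untested when both other arms lie in between (minor)

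*SAP*

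**What the plan says.** SAP section 9.1 (adverse events) sets a two-step rule. Step one: "First, an overall Fisher's Exact test will be carried out to compare each safety parameter among all four treatment groups". Step two starts with "If this overall test is significant", at p ≤ 0.05, and then "pairwise comparisons will be carried out to compare the 3M Oral Rinse and the vehicle control". The level for step two is given by "Each active vs vehicle comparison will be carried out at an alpha level of 0.05"; sidedness is not stated. SAP section 9.2 repeats the rule for side effects recorded in the diary.

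Protocol section 11.6 has the same sequence without naming the test: "First, an overall test will be carried out to compare each safety parameter among all four treatment groups". It lists abnormal oral tissue findings among the safety variables. SAP section 9.3 plans only summaries and shift tables for them.

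The descriptive output does not depend on the overall test. Treatment-emergent adverse events "will be summarized by severity, relatedness, overall and treatment group", with verbatim listings and separate summaries of serious events, and side effects are tabulated by week and group. No section plans a risk difference or confidence interval for any safety parameter.

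**The concern.** The safety objective (SAP 2.2, protocol 5.5) concerns the 3M rinse, and protocol 9.1 makes adverse event incidence the principal safety measure. An overall test placed in front of pairwise tests usually limits false positives across several comparisons. Here only one comparison is named behind it. The two arms outside that comparison therefore determine whether it is made.

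The efficacy plan works differently. SAP 8.1 sets the other two arms aside for the primary 3M-versus-vehicle comparison, and the Tukey-adjusted comparisons in SAP 8.3 have no preceding overall test. Only safety carries this condition, although a missed difference is usually the costlier error in a safety screen. At stake is a modest loss of power for the one safety contrast that the plan singles out.

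**Working it through.** **Inputs.** Planned size: "To account for possible dropouts, a sample size of 50 subjects per group will be recruited" (SAP 6.1). Allocation: "The randomization ratio was 1:1:1:1 among the four treatment groups" (SAP 3.2). Both levels are 0.05 (SAP 9.1). I assume a two-sided pairwise test. The documents give no event rates, so every rate below is an assumption.

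**The plan's own figure.** The only sample-size figure is for efficacy. The normal approximation is n = 2(1.960 + 1.282)² × 0.5² / 0.40² = 32.8, so 33 per group. The t-test version gives 33.8, so the stated 34 is reproduced. It says nothing about safety power; only the 50 per arm carries over.

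**Tests.** For counts x₁ to x₄ out of 50 with total T, the probability of a table given its margins is ∏C(50, xᵢ) / C(200, T). The overall exact p-value sums this over all tables with the same T that are no more probable than the one observed. The pairwise p-value is the two-sided 2×2 Fisher test.

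| 3M, vehicle, PerioShield, water | Pairwise p | Overall p | 3M vs vehicle tested? |
|---|---|---|---|
| 10, 2, 5, 5 | 0.028 | 0.094 | no |
| 10, 2, 5, 2 | 0.028 | 0.029 | yes |
| 10, 2, 2, 2 | 0.028 | 0.011 | yes |
| 6, 0, 3, 3 | 0.027 | 0.079 | no |
| 13, 3, 8, 8 | 0.012 | 0.054 | no |
| 23, 10, 16, 17 | 0.010 | 0.053 | no |
| 12, 2, 7, 7 | 0.008 | 0.035 | yes |

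The first three rows have identical 3M and vehicle data; only the other arms change the outcome.

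**Why.** If both other arms sit exactly at the midpoint p̄, they add nothing to the Pearson statistic. The four-arm and two-arm statistics are then both n·d² / [2p̄(1 − p̄)], where d is the 3M-minus-vehicle difference. For 10, 2, 6, 6 this is 50 × 0.16² / (2 × 0.12 × 0.88) = 6.06. That exceeds the 1-df critical value of 3.84 but not the 3-df value of 7.81. On this approximate scale the pairwise threshold drops from 0.05 to about 0.005. With the more conservative exact tests, the pairwise p-values blocked in such patterns run from about 0.01 to 0.05.

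**Power.** I summed ∏Bin(xᵢ; 50, πᵢ) over all 51⁴ tables with pairwise p ≤ 0.05, then over those that also have overall p ≤ 0.05. Losses are taken before rounding.

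| Pattern | True rates, % (3M/vehicle/PerioShield/water) | Pairwise alone | With condition | Loss, points |
|---|---|---|---|---|
| Both in between | 20/4/10/10 | 59.4% | 51.0% | 8.4 |
| | 24/6/15/15 | 63.3% | 52.6% | 10.8 |
| | 30/10/20/20 | 64.0% | 51.5% | 12.5 |
| | 40/20/30/30 | 51.5% | 38.5% | 13.0 |
| Only PerioShield in between | 20/4/10/4 | 59.4% | 56.8% | 2.7 |
| | 24/6/15/6 | 63.3% | 60.2% | 3.1 |
| | 30/10/20/10 | 64.0% | 59.4% | 4.6 |
| | 40/20/30/20 | 51.5% | 44.3% | 7.2 |
| PerioShield equal to 3M | 20/4/20/4 | 59.4% | 58.7% | 0.7 |
| Harm in 3M only | 20/4/4/4 | 59.4% | 58.1% | 1.4 |
| | 30/10/10/10 | 64.0% | 61.0% | 3.1 |

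**Price of dropping the condition.** With all four rates at 10%, the chance of a nominally significant 3M-versus-vehicle result is 1.8% without the condition and 1.2% with it, per parameter.

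**What an estimate would show.** For 10/50 against 2/50 the risk difference is 0.20 − 0.04 = 0.16. The Wilson limits are (0.112, 0.330) and (0.011, 0.135). The Newcombe 95% interval is therefore 0.16 − √(0.088² + 0.095²) to 0.16 + √(0.130² + 0.029²), about 3 to 29 points.

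**The case against.** The strongest reply is that the larger losses need sterile water to produce more events than the vehicle. Protocol 7.5 treats water and vehicle as the two negative controls, and nothing in the documents suggests such an ordering of true rates. This stands. If water tracks vehicle, the loss is mostly 3 to 5 points. Chance can still place observed water counts between the other arms at 50 per group, but the 8-to-13-point figures are not the expected case.

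A reader might infer that any clear imbalance against vehicle goes untested. The documents do not support that: stronger imbalances such as 12, 2, 7, 7 reach the pairwise test, and those blocked have pairwise p-values of about 0.01 to 0.05. A reader might also infer that harm would be hidden, or reported as not significant. That is unsupported too. When the overall test fails, the comparison is simply not made. The summaries and listings are still produced, and a split of 10 against 2 would be seen. Study success rests on the plaque and gingival indices alone.

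Finally, an overall test before pairwise tests is a conventional, prespecified procedure. With many safety parameters, limiting chance findings is a legitimate aim, so this is a trade-off and not an error. The plural wording in step two could hint that PerioShield versus vehicle was also in mind, but only 3M versus vehicle is named. None of this supplies the missing interval estimate.

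**Conclusion.** The concern holds as a minor point. The condition can leave a nominally significant 3M-versus-vehicle difference untested, and whether it does depends on arms outside the comparison.

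The size depends on the pattern. The loss is about 8 to 13 points if both PerioShield and water truly exceed vehicle. If only PerioShield does, it is about 3 to 5 points (7 at the highest rates tried). If harm is confined to 3M, it is about 1 to 3 points. These figures assume 50 evaluable subjects per arm, a two-sided pairwise Fisher test and event rates that the documents do not give.

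The firmer part of the finding needs no assumed rates: whatever the overall test shows, the plan gives no interval estimate for the safety contrast that it singles out.

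**What to change.** In SAP 9.1 and 9.2 and protocol 11.6, remove the overall test as a precondition. For each safety parameter, always report the 3M-versus-vehicle risk difference with a 95% confidence interval (method named) and a two-sided Fisher p-value labelled nominal and unadjusted. Keep the four-arm test as descriptive. State whether the same applies to the oral tissue findings, which protocol 11.6 includes and SAP 9.3 only summarises.

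The cost is a wording change and a few table columns, using data already collected. Efficacy alpha and sample size are untouched. The downside is slightly more nominal false-positive safety signals, as the null calculation above shows; the labelling deals with that.

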2.2 Secondary Objectives

- To investigate the effects of the 3M Oral Rinse vs. Placebo Vehicle Control on plaque and gingivitis, at 3 months, based on the Modified Quigley-Hein Plaque Index (PI) and the Löe-Silness Gingival Index (GI) scores.
- To investigate the effects of the 3M Oral Rinse vs. Placebo Vehicle Control on Eastman Interdental Bleeding Index (BI) scores at 3 and 6 months
- To investigate the relative efficacy, using pairwise comparisons, of the four treatment groups, namely 3M Oral rinse, vehicle control, PerioShield (predicate) and water control, with respect to the PI and GI scores at 6 months.
- To assess the safety of the 3M oral rinse by tracking abnormal changes to soft and hard tissues, reported side effects and adverse events during the study.

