9.3 Soft and Hard Oral Tissue Assessment

The incidence of normal and abnormal soft and hard tissue findings will be summarized by visit and treatment group. Shifts in findings from normal/abnormal to normal/abnormal observed within the first 3 months will be summarized by treatment group. The worst assessment up to the 3-month visit will be used in this summary. In addition, shifts in findings from normal/abnormal to normal/abnormal between the baseline visit and the last available visit will be summarized by treatment group.

Revision History

Revision Details:

- 1 To establish statistical analysis plan before study enrollment.
- 2
 - (1) To clarify when per protocol dataset will be applied (Section 5.3).
 - (2) To clarify dosing compliance computation (Section 7.4)
 - (3) To indicate the classification of AEs using the MedDRA dictionary (Section 9.1)
 - (4) To clarify the incorporation of the unscheduled oral assessment data in planned summaries (Section 9.3).

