7.5 Choice of Comparator

The comparators are two negative controls (water and vehicle oral rinse) and a positive control, PerioShield Oral Health Rinse, the predicate medical device.

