9. ASSESSMENT OF SAFETY

9.1 Safety Parameters

The principal measure of safety will be the incidence of adverse events reported during the study.

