9.3 Adverse Events

An adverse event (AE) can be identified via visual examination by the dental examiner or reported by the subject. The Investigator is responsible for identifying AEs throughout the study. An AE may occur at any time during the conduct of the study, in any phase of the study or after the study is completed.

Examples of AEs that are considered expected during the conduct of the study include the following: mucosal sloughing, taste alteration, mouth or tongue numbness or tingling, and dry mouth. In addition, irritated or bleeding gums may occur due to probing during the dental examination.

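### Minor: safety comparisons stop at a gated 3M-versus-vehicle test, so no planned output estimates the 3M rinse's excess of adverse events over water

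*SAP*

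**What the plan says.** The safety objective covers the whole product: "To assess the safety of the 3M oral rinse by tracking abnormal changes to soft and hard tissues", together with side effects and adverse events (SAP 2.2; protocol 5.5 is the same). Protocol 9.1 adds: "The principal measure of safety will be the incidence of adverse events reported during the study".

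SAP 9.1 (adverse events) and SAP 9.2 (diary side effects) set two steps. The first is a Fisher exact test across the four groups for each parameter. If p ≤ 0.05, "pairwise comparisons will be carried out to compare the 3M Oral Rinse and the vehicle control". Protocol 11.6 has the same sequence without naming the overall test, and extends it to abnormal oral tissue. All three sections add: "Each active vs vehicle comparison will be carried out at an alpha level of 0.05". That looser wording could also cover PerioShield versus vehicle. It does not cover 3M versus water.

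Water has a stated role. Protocol 7.5 says: "The comparators are two negative controls (water and vehicle oral rinse) and a positive control". For plaque and gingival index at 6 months, SAP 8.3 and protocol 11.5 plan "All pairwise comparisons involving the four treatment groups", which includes 3M versus water.

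SAP 9.3 gives descriptive tissue summaries by visit and group and two shift tables. The first covers the first 3 months: "The worst assessment up to the 3-month visit will be used in this summary". The second runs from baseline to the last available visit.

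**The concern.** A rinse and its vehicle share everything except the active component. If the shared part causes irritation or taste change, the two arms move together and their difference stays near zero. The contrast that would show this is 3M against water. It is planned for benefit and not for harm.

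Two report patterns could then be misread as reassurance about the product. In one, a significant four-group test is followed by a null 3M-versus-vehicle test. In the other, the four-group test is not significant and no pairwise result follows. Neither states how large an excess over water the data leave open.

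Protocol 9.3 names the events it expects: "mucosal sloughing, taste alteration, mouth or tongue numbness or tingling, and dry mouth". It does not attribute them to the vehicle, so harm shared with the vehicle is a possibility to plan for and not a finding.

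**Working it through.** **What the plan computes.** No safety sample size, event rate or margin is stated. The only power figure, 34 per group, is for efficacy (difference 0.40, SD 0.5, one-sided 0.025). It reproduces: noncentral-t power is 90.2% at 34 and 89.3% at 33. It has no bearing on safety.

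**Inputs.** 50 per arm (SAP 6.1), with all randomized subjects in the safety analysis (protocol 11.2). Alpha is 0.05. Sidedness is not stated, so two-sided Fisher tests are assumed. All event rates are assumptions. The order is always 3M/vehicle/PerioShield/water.

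**Interval method.** Newcombe hybrid score. For d = p1 − p2 with Wilson limits (l, u) for each arm:

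- lower = d − √[(p1 − l1)² + (u2 − p2)²]
- upper = d + √[(u1 − p1)² + (p2 − l2)²]

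**Example (a): 10/10/2/2 events.** The Wilson limits are 0.112 to 0.330 for 10/50 and 0.011 to 0.135 for 2/50.

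- 3M minus water: d = 0.20 − 0.04 = 0.16
- lower = 0.16 − √(0.0876² + 0.0946²) = 0.16 − 0.129 = 0.031
- upper = 0.16 + √(0.1304² + 0.0290²) = 0.16 + 0.134 = 0.294
- Fisher p for 3M versus water = 0.028
- 3M minus vehicle = 0 (−15.7 to +15.7 points)
- Four-group p = 0.006

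The planned output is a significant overall test and then a null follow-up.

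**Example (b): 5/5/2/2 events.** Four-group p = 0.48, so no pairwise result is planned. 3M minus water is +6 points (−5.0 to +17.7), p = 0.44. An excess of nearly 18 points is not excluded, and no planned output says so.

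**Chance that each test is significant** (exact enumeration of all outcomes). The planned step requires both the four-group test and 3M versus vehicle to be significant. 3M versus water is ungated.

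| True rates, % | Four-group test | Planned 3M v vehicle step | 3M v water |
|---|---|---|---|
| 5/5/1/1 | 15% | 0.7% | 2% |
| 10/10/5/5 | 16% | 1.5% | 6% |
| 10/10/2/2 | 49% | 1.8% | 19% |
| 20/20/4/4 | 88% | 2.8% | 59% |
| 20/20/20/4 | 73% | 2.8% | 59% |
| 20/12/4/4 (partly shared) | 73% | 12% | 59% |

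Where 3M equals vehicle, the low third column is a true null that is not rejected. It shows only that this contrast carries no information on shared harm. The four-group figure depends on the rate given to PerioShield (88% against 73% in the 20% rows). The water column does not.

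**What an interval would show.** Mean 95% limits for 3M minus water are −4.6 to +13.7 points at 5 v 1%, −6.2 to +16.7 at 10 v 5%, and +3.3 to +29.3 at 20 v 4%. At low rates a test against water is nearly always null too, so the useful output is the interval.

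**Chance findings.** With equal true rates of 5, 10 or 20%, an interval lies wholly above zero in 1.1, 1.8 or 2.4% of trials. Two intervals per parameter over an assumed 20 parameters give 20 × 2 × 0.011 = 0.4 to 20 × 2 × 0.024 = 1.0 expected false adverse signals. Eight parameters give 8 × 2 × 0.011 = 0.2 to 8 × 2 × 0.024 = 0.4.

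**Shift tables.** Suppose an unscheduled oral exam after month 3 (allowed by protocol 9.2 and the study schedule) finds an abnormality that has resolved by the last visit. The first table has closed at month 3, and the second reads normal at the last visit. The abnormality enters neither. No magnitude is claimed.

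**The case against.** The strongest reply is that nothing here is an error. The objective is met by tracking findings and events. The principal measure is incidence, and all-pairs comparison is promised for plaque and gingival index only, so leaving it out of safety breaks no commitment. Vehicle is a sound comparator for the active ingredient and matches the efficacy comparator. This stands.

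Much of the information is also already planned. Adverse events are tabulated by severity, relatedness and group, side effects by week and group, and tissue findings by visit and group. Relatedness is judged to the device as a whole, and water is in the overall test. In example (a) the table would visibly separate 3M and vehicle from water. This stands too. What the tables lack is the difference and its uncertainty, which matters at 50 per arm.

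A reader might infer that the plan would hide or miss harm from the vehicle, or that vehicle is the wrong safety comparator. The documents support neither. The summaries and the four-group test can expose such a signal, and no event is attributed to the vehicle. A reader might also take the 1 to 3% figures for the vehicle step as poor power. They are not, because there is no 3M-versus-vehicle difference to detect in those rows.

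The shift-table gap needs a late, transient abnormality seen only at an unscheduled exam. It could still appear in the by-visit incidence, the case report form description or the adverse event listing.

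**Conclusion.** The point holds as a minor, cheap improvement. The planned pairwise safety follow-up is a gated test against vehicle, which carries no information on an effect the vehicle shares. No safety difference or interval is planned for any pair, so the excess over water would be visible only as raw incidences.

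The size depends on assumed rates. An interval against water is clearly informative when the excess is large (20 v 4%), where the four-group test already fires in 73 to 88% of trials depending on PerioShield's rate. At low rates its value is in stating how much excess is not excluded. Shared harm itself remains an assumption. The shift-table gap is a separate, smaller matter.

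**What to change.** Keep the planned tests and gate. In SAP 9.1, SAP 9.2 and protocol 11.6, add 3M-minus-water and 3M-minus-vehicle risk differences with 95% CIs, ungated, labelled nominal and led by the estimate. Prespecify a short list:

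- any treatment-emergent adverse event
- any related adverse event
- each expected event named in protocol 9.3
- any diary side effect over the whole treatment period, not by week

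This is about eight parameters if gum irritation or bleeding from probing is counted. State that a null result against either comparator does not show absence of harm.

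Separately, in SAP 9.3, extend the worst-assessment shift table from baseline through month 6, including unscheduled visits.

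The cost is wording, two estimate columns and one extended table, from data already collected. The downside is some chance findings: about 0.2 to 0.4 expected false adverse signals on a list of eight, against 0.4 to 1.0 on an assumed 20, at equal true rates of 5 to 20%.
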